5.2.2 Serious Adverse Events (Immediately Reportable to the Sponsor)

A serious adverse event is any adverse event that meets any of the following criteria:

- Is fatal (i.e., the adverse event actually causes or leads to death)
- Is life threatening (i.e., the adverse event, in the view of the investigator, places the patient at immediate risk of death)

This does not include any adverse event that had it occurred in a more severe form or was allowed to continue might have caused death.

- Requires or prolongs inpatient hospitalization (see Section 5.3.5.10)
- Results in persistent or significant disability/incapacity (i.e., the adverse event results in substantial disruption of the patient's ability to conduct normal life functions)
- Is a congenital anomaly/birth defect in a neonate/infant born to a mother exposed to study drug
- Is a significant medical event in the investigator's judgment (e.g., may jeopardize the patient or may require medical/surgical intervention to prevent one of the outcomes listed above)

The terms "severe" and "serious" are not synonymous. Severity refers to the intensity of an adverse event (e.g., rated as mild, moderate, or severe, or according to National Cancer Institute Common Terminology Criteria for Adverse Events (NCI CTCAE) criteria;

see Section 5.3.3); the event itself may be of relatively minor medical significance (such as severe headache without any further findings).

Severity and seriousness need to be independently assessed for each adverse event recorded on the eCRF.

Serious adverse events are required to be reported by the investigator to the Sponsor immediately (i.e., no more than 24 hours after learning of the event; see Section 5.4.2 for reporting instructions).

5.2.3 Non-Serious Adverse Events of Special Interest (Immediately Reportable to the Sponsor)

Non-serious adverse events of special interest are required to be reported by the investigator to the Sponsor immediately (i.e., no more than 24 hours after learning of the event; see Section 5.4.2 for reporting instructions). Adverse events of special interest for this study include the following:

- The following are confirmed treatment-emergent autoimmune conditions:
 - Pneumonitis
 - Colitis
 - Endocrinopathies: diabetes mellitus, pancreatitis, adrenal insufficiency or hyperthyroidism
 - Hepatitis
 - Transaminitis: Grade ≥ 2 (AST or ALT $> 3 \times$ ULN and bilirubin $> 2 \times$ ULN) or AST/ALT $> 10 \times$ ULN
 - Systemic lupus erythematosus
 - Neurological: Guillain-Barré syndrome, Myasthenia Gravis, Meningoencephalitis
- Events suggestive of hypersensitivity, cytokine release, SIRS (influenza-like illness, systemic inflammatory response syndrome), SIA (systemic inflammatory activation) or infusion-reaction syndromes"
- Cases of potential drug-induced liver injury that include an elevated ALT or AST in combination with either an elevated bilirubin or clinical jaundice, as defined by Hy's law (see Section 5.3.5.6)
- Suspected transmission of an infectious agent by the study drug, as defined below
 - Any organism, virus, or infectious particle (e.g., prion protein transmitting transmissible spongiform encephalopathy), pathogenic or non-pathogenic, is considered an infectious agent. A transmission of an infectious agent may be suspected from clinical symptoms or laboratory findings that indicate an infection in a patient exposed to a medicinal product. This term applies only when a contamination of the study drug is suspected."

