5.1.1 Risks Associated With Atezolizumab

The PD-L1/PD-1 pathway is involved in peripheral tolerance; therefore, such therapy may increase the risk of immune-mediated adverse events, specifically the induction or enhancement of autoimmune conditions.

Atezolizumab has been associated with risks such as the following: IRRs and immune-mediated hepatitis, pneumonitis, colitis, pancreatitis, diabetes mellitus, hypothyroidism, hyperthyroidism, adrenal insufficiency, hypophysitis, Guillain-Barré syndrome, myasthenic syndrome or myasthenia gravis, meningoencephalitis, myocarditis, nephritis, and myositis. Immune-mediated reactions may involve any organ system and may lead to hemophagocytic lymphohistiocytosis and macrophage activation syndrome.

Refer to Appendix 8 and Section 6 of the Atezolizumab Investigator's Brochure for a detailed description of anticipated safety risks for atezolizumab.

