4.7.2 Adverse Events

Adverse events (AE) will be coded using MedDRA.

AEs will be graded according to the National Cancer Institute Common Terminology Criteria for Adverse Events (NCI CTCAE), Version 4.0. For events of varying severity, the most severe grade as documented on the eCRF will be used in the summaries.

The analysis will focus on treatment-emergent AEs – AEs which start on or after the date of first dose of study drug. (For the assignment of ‘treatment-emergent’ in case of incomplete dates being recorded on the CRF, see Section 4.8.)

AEs of Special Interest are defined according to current Roche global guidelines, and are identified in the clinical database. (This classification overrides the flag set in the eCRF by the Investigator.)

An overview that summarizes the number of patients with treatment-emergent AEs (and the number of events) will be provided including all AEs, related AEs, AEs of Special Interest (AESI), Serious AEs (SAEs), related SAEs, SAEs leading to death, related SAEs leading to death and AEs leading to treatment discontinuation. The number of patients experiencing AEs at each grade (by highest grade) and related AEs at each grade (by highest grade) will also be included.

The number and frequency of patients with treatment-emergent AEs will be presented by primary System Organ Class (SOC) and Preferred Term (PT) within SOC, both overall and for highest grade within patient, for the following:

- All AEs

- Related AEs [“All combined” only]
- AESIs (by AESI class and PT rather than by SOC and PT) [“All combined” only]
- SAEs [“All combined” only]
- Related SAEs [“All combined” only]
- SAEs leading to death [“All combined” only]
- Related SAEs leading to death [“All combined” only]

In addition, a summary of non-serious AEs occurring in 5% or more of patients will be provided (for regulatory disclosure purposes), for “All combined” only.

Patient listings will be provided for:

- AEs leading to treatment discontinuation or interruption
- AESIs
- SAEs
- All deaths.

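### The Protocol 5.2.3 list of events of special interest does not name seven of the 18 risks in 5.1.1; for five of them nothing else in the list covers a non-serious case

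*Protocol*

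**What the plan says.** Protocol 5.1.1 lists the risks associated with atezolizumab in three runs: "IRRs and immune-mediated hepatitis, pneumonitis, colitis, pancreatitis, diabetes mellitus, hypothyroidism, hyperthyroidism"; then "adrenal insufficiency, hypophysitis, Guillain-Barré syndrome, myasthenic syndrome or myasthenia gravis, meningoencephalitis, myocarditis, nephritis, and myositis"; and it adds that immune-mediated reactions "may lead to hemophagocytic lymphohistiocytosis and macrophage activation syndrome".

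Protocol 5.2.3 lists the non-serious adverse events of special interest (AESIs) that an investigator must report to the sponsor within 24 hours. Its endocrine line is "Endocrinopathies: diabetes mellitus, pancreatitis, adrenal insufficiency or hyperthyroidism" and its neurological line is "Neurological: Guillain-Barré syndrome, Myasthenia Gravis, Meningoencephalitis". It also names pneumonitis, colitis, hepatitis, transaminitis and systemic lupus erythematosus. A systemic line covers events suggestive of hypersensitivity, cytokine release and SIRS and ends with "SIA (systemic inflammatory activation) or infusion-reaction syndromes". Potential drug-induced liver injury and suspected transmission of an infectious agent complete the list.

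Protocol 5.4 gives three classes of event with a 24-hour duty: serious adverse events, non-serious AESIs and pregnancies. Section 5.1.2.2 likewise ties expedited reporting to serious events and the AESIs that the protocol defines.

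For the analysis, SAP 4.7.2 takes its definition from elsewhere: "AEs of Special Interest are defined according to current Roche global guidelines". That classification overrides the investigator's eCRF flag.

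**The concern.** Section 5.2.3 is the only place where the protocol gives a non-serious immune-mediated event a 24-hour duty. If a condition that the protocol itself calls a drug risk is not on the list, a non-serious case is recorded on the Adverse Event eCRF under 5.3.1 like any other event. It also falls outside the prompt sponsor evaluation in 5.7, which covers serious events and non-serious AESIs.

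The sections appear not to have been brought into line. Section 5.1.1 includes "meningoencephalitis, myocarditis, nephritis, and myositis", and Appendix 8 devotes a management table to each of these, yet 5.2.3 takes up only the first. SIA remains on the list although the current protocol body no longer describes it elsewhere, while HLH and MAS, which Appendix 8 does define, are not listed. At stake is how early the sponsor sees non-serious cases. No efficacy endpoint or stopping rule is involved.

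**Working it through.** No sample size or error rate is involved. The check is a comparison of two lists in the current text, and it does not rest on the amendment summary.

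**Step 1. Count the risks in 5.1.1.** The first run has 8, the second 8 (myasthenic syndrome or myasthenia gravis taken as one), and the last 2. 8 + 8 + 2 = 18.

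**Step 2. Match them to 5.2.3.**

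| Run in 5.1.1 | Named in 5.2.3 | Not named in 5.2.3 |
|---|---|---|
| First (8) | infusion-related reactions, hepatitis, pneumonitis, colitis, pancreatitis, diabetes mellitus, hyperthyroidism (7) | hypothyroidism (1) |
| Second (8) | adrenal insufficiency, Guillain-Barré syndrome, myasthenia gravis, meningoencephalitis (4) | hypophysitis, myocarditis, nephritis, myositis (4) |
| Last (2) | none (0) | HLH, MAS (2) |

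Named: 7 + 4 + 0 = 11. Not named: 18 − 11 = 7.

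**Step 3. Look for wording that could cover the seven anyway.** The systemic line is broad enough that some HLH or MAS cases could be reported under cytokine release, SIRS or SIA. No line of 5.2.3 plausibly covers the other five. Clean gap: 7 − 2 = 5, namely myocarditis, myositis, nephritis, hypophysitis and hypothyroidism.

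**Step 4. Look for another route to the sponsor.** Section 5.4 offers none with a time limit for a non-serious, unlisted event. Appendix 8 has guidance for all seven and asks for Medical Monitor contact as follows, in no case with a time limit:

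| Condition (Appendix 8 table) | Contact asked for | Contact not asked for, or conditional |
|---|---|---|
| Myocarditis (Table 6) | Grades 2 to 4 | Grade 1: none |
| Myositis (Table 13) | Grades 2 to 4 | Grade 1: none |
| Nephritis, as renal events (Table 12) | Grades 3 and 4 | Grade 1: none; Grade 2: only if unresolved |
| Hypophysitis (Table 4) | Grade 4 | Grades 2 and 3: only if unresolved |
| Hypothyroidism (Table 4) | never | symptomatic and asymptomatic: none |
| Suspected HLH or MAS (Table 14) | always | – |

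**Step 5. Check SIA.** Section 5.2.3 expands it as in "SIA (systemic inflammatory activation) or infusion-reaction syndromes". The abbreviation list expands it as systemic immune activation. Neither Section 5.1.4 nor Appendix 8 describes it.

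**The case against.** The strongest reply is that the practical gap is small. Serious cases of all seven conditions go to the sponsor within 24 hours, including through the significant-medical-event criterion in 5.2.2. From Grade 2, myocarditis and myositis call for Medical Monitor contact, as does any suspected HLH or MAS. So a reader might infer that Grade 1 or 2 cases never reach the sponsor promptly, and the documents do not support that. What stands is that the contact has no time limit, is absent or conditional at the lower grades in the table above, and is not an AESI report. The significant-medical-event criterion depends on the investigator's judgment.

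Second, nothing says that the AESI list must equal the risk list. The endocrine line names hyperthyroidism specifically, and asymptomatic hypothyroidism does not interrupt treatment under Appendix 8, so leaving hypothyroidism out may be a choice. That is fair, but the protocol does not say so. It is a weak explanation for myocarditis, myositis, nephritis and hypophysitis.

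Third, the list is introduced as what AESIs include, which could be read as open-ended. The endocrine and neurological lines nevertheless enumerate diagnoses, and nothing else in the protocol brings the missing ones in.

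Fourth, a reader might infer from SAP 4.7.2 that the AESIs collected from sites differ from those analysed. The documents show two sources for the definition. They do not show different contents, because the sponsor guideline is not reproduced. All adverse events after the start of study drug are recorded through the reporting period in 5.3.1, and the SAP identifies AESIs in the clinical database, so no loss from the analysis is shown. That arrangement gives sites no 24-hour duty, however.

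Fifth, the differing SIA expansions are editorial, and the marking of the abbreviation-list entry may be an artefact of reading the PDF. The mismatch deserves correction but carries little weight.

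**Conclusion.** The point holds in limited form. Section 5.2.3 leaves seven of the 18 risks in 5.1.1 unnamed. For five of these no other wording in the list helps, and for one of the five, hypothyroidism, the omission may be intended. HLH and MAS are unnamed but possibly captured in part. The consequence is confined to non-serious cases, and to the speed and certainty with which the sponsor hears of them.

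The size in patients cannot be given, because the documents contain no rate of non-serious cases for these conditions. The count assumes that myasthenic syndrome and myasthenia gravis are one risk, that the infusion-reaction wording covers infusion-related reactions, and that HLH and MAS are two.

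A reader might go further and ask that every condition in Appendix 8 be expedited. The contradiction does not support that. It lies between 5.1.1 and 5.2.3, and Appendix 8 also covers events, such as mild rash, that 5.1.1 does not list. The primary endpoint, the cohort decisions and the stopping rules are unaffected.

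**What to change.** Reconcile 5.2.3 with 5.1.1:

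- Add at least myocarditis, myositis, nephritis, hypophysitis, HLH and MAS.
- Add hypothyroidism, or state in one sentence why it is excluded.
- Replace SIA, or define it once and expand it the same way in 5.2.3 and the abbreviation list.
- Have the protocol and SAP 4.7.2 cite the same AESI definition, by version, so that sites and the analysis work from one list.

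The text change is short, but it is a protocol amendment. Section 9.6 requires IRB/EC approval, and regulatory approval where locally required, before implementation, and 9.4 foresees about 50 sites. A site notice and some additional expedited reports follow; their number cannot be estimated from the documents. The change concerns reporting only and leaves dosing and clinical management as they are.

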5.3 METHODS AND TIMING FOR CAPTURING AND ASSESSING SAFETY PARAMETERS

The investigator is responsible for ensuring that all adverse events (see Section [5.2.1](#) for definition) are recorded on the Adverse Event eCRF and reported to the Sponsor in accordance with instructions provided in this section and in Section [5.4-5.6](#).

For each adverse event recorded on the Adverse Event eCRF, the investigator will make an assessment of seriousness (see Section [5.2.2](#) for seriousness criteria), severity (see Section [5.3.3](#)), and causality (see Section [5.3.4](#)).

5.3.1 Adverse Event Reporting Period

Investigators will seek information on adverse events at each patient contact. All adverse events, whether reported by the patient or noted by study personnel, will be recorded in the patient's medical record and on the Adverse Event eCRF.

After informed consent has been obtained **but prior to initiation of study drug**, only serious adverse events caused by a protocol-mandated intervention (e.g., invasive procedures such as biopsies, discontinuation of medications) should be reported (see Section [5.4.2](#) for instructions for reporting serious adverse events).

After initiation of study drug, all adverse events will be reported until 90 days after the last dose of study drug or until they receive another anti-cancer therapy, whichever comes first. After this period, the investigator should report any serious adverse events that are believed to be related to prior study drug treatment (see Section [5.6](#)).

5.3.2 Eliciting Adverse Event Information

A consistent methodology of non-directive questioning should be adopted for eliciting adverse event information at all patient evaluation timepoints. Examples of nondirective questions include the following:

"How have you felt since your last clinic visit?"

"Have you had any new or changed health problems since you were last here?"

5.3.3 Assessment of Severity of Adverse Events

The adverse event severity grading scale for the NCI CTCAE (v4.0) will be used for assessing adverse event severity. [Table 6](#) will be used for assessing severity for adverse events that are not specifically listed in the NCI CTCAE.

Table 6. Adverse Event Severity Grading Scale for Events Not Specifically Listed in NCI CTCAE

Grade	Severity
1	Mild; asymptomatic or mild symptoms; clinical or diagnostic observations only; or intervention not indicated
2	Moderate; minimal, local, or non-invasive intervention indicated; or limiting age-appropriate instrumental activities of daily living ^a
3	Severe or medically significant, but not immediately life-threatening; hospitalization or prolongation of hospitalization indicated; disabling; or limiting self-care activities of daily living ^{b,c}
4	Life-threatening consequences or urgent intervention indicated ^d
5	Death related to adverse event ^d

NCI CTCAE = National Cancer Institute Common Terminology Criteria for Adverse Events.

Note: Based on the most recent version of NCI CTCAE (v4.0), which can be found at:

http://ctep.cancer.gov/protocolDevelopment/electronic_applications/ctc.htm

^a Instrumental activities of daily living refer to preparing meals, shopping for groceries or clothes, using the telephone, managing money, etc.

^b Examples of self-care activities of daily living include bathing, dressing and undressing, feeding oneself, using the toilet, and taking medications, as performed by patients who are not bedridden.

^c If an event is assessed as a "significant medical event," it must be reported as a serious adverse event (see Section 5.4.2 for reporting instructions), per the definition of serious adverse event in Section 5.2.2.

^d Grade 4 and 5 events must be reported as serious adverse events (see Section 5.4.2 for reporting instructions), per the definition of serious adverse event in Section 5.2.2.

5.3.4 Assessment of Causality of Adverse Events

Investigators should use their knowledge of the patient, the circumstances surrounding the event, and an evaluation of any potential alternative causes to determine whether or not an adverse event is considered to be related to the study drug, indicating "yes" or "no" accordingly. The following guidance should be taken into consideration

- Temporal relationship of event onset to the initiation of study drug
- Course of the event, considering especially the effects of dose reduction, discontinuation of study drug, or reintroduction of study drug (as applicable)
- Known association of the event with the study drug or with similar treatments
- Known association of the event with the disease under study
- Presence of risk factors in the patient or use of concomitant medications known to increase the occurrence of the event
- Presence of non-treatment-related factors that are known to be associated with the occurrence of the event

For patients receiving combination therapy, causality will be assessed individually for each protocol-mandated therapy.

5.3.5 Procedures for Recording Adverse Events

Investigators should use correct medical terminology/concepts when recording adverse events on the Adverse Event eCRF. Avoid colloquialisms and abbreviations.

Only one adverse event term should be recorded in the event field on the Adverse Event eCRF.

5.3.5.1 Diagnosis versus Signs and Symptoms

For adverse events other than infusion-related reactions, a diagnosis (if known) should be recorded on the Adverse Event eCRF rather than individual signs and symptoms (e.g., record only liver failure or hepatitis rather than jaundice, asterixis, and elevated transaminases). However, if a constellation of signs and/or symptoms cannot be medically characterized as a single diagnosis or syndrome at the time of reporting, each individual event should be recorded on the Adverse Event eCRF. If a diagnosis is subsequently established, all previously reported adverse events based on signs and symptoms should be nullified and replaced by one adverse event report based on the single diagnosis, with a starting date that corresponds to the starting date of the first symptom of the eventual diagnosis.

5.3.5.2 Adverse Events That Are Secondary to Other Events

In general, adverse events that are secondary to other events (e.g., cascade events or clinical sequelae) should be identified by their primary cause, with the exception of severe or serious secondary events. A medically significant secondary adverse event that is separated in time from the initiating event should be recorded as an independent event on the Adverse Event eCRF. For example:

- If vomiting results in mild dehydration with no additional treatment in a healthy adult, only vomiting should be reported on the eCRF.
- If vomiting results in severe dehydration, both events should be reported separately on the eCRF.
- If a severe gastrointestinal hemorrhage leads to renal failure, both events should be reported separately on the eCRF.
- If dizziness leads to a fall and consequent fracture, all three events should be reported separately on the eCRF.
- If neutropenia is accompanied by an infection, both events should be reported separately on the eCRF.

All adverse events should be recorded separately on the Adverse Event eCRF if it is unclear as to whether the events are associated.

5.3.5.3 Persistent or Recurrent Adverse Events

A persistent adverse event is one that extends continuously, without resolution, between patient evaluation timepoints. Such events should only be recorded once on the Adverse Event eCRF. The initial severity (intensity or grade) of the event will be recorded at the time the event is first reported. If a persistent adverse event becomes more severe, the most extreme severity should also be recorded on the Adverse Event eCRF. If the event becomes serious, it should be reported to the Sponsor immediately (i.e., no more than 24 hours after learning that the event became serious; see Section 5.4.2 for reporting instructions). The Adverse Event eCRF should be updated by changing the event from "non-serious" to "serious," providing the date that the event became serious, and completing all data fields related to serious adverse events.

A recurrent adverse event is one that resolves between patient evaluation timepoints and subsequently recurs. Each recurrence of an adverse event should be recorded as a separate event on the Adverse Event eCRF.

5.3.5.4 Abnormal Laboratory Values

Not every laboratory abnormality qualifies as an adverse event. A laboratory test result must be reported as an adverse event if it meets any of the following criteria:

- Change from baseline and one of the following:
- Is accompanied by clinical symptoms
- Results in a change in study treatment (e.g., dosage modification, treatment interruption, or treatment discontinuation)
- Results in a medical intervention (e.g., potassium supplementation for hypokalemia) or a change in concomitant therapy
- Is clinically significant in the investigator's judgment

Note: For oncology trials, certain abnormal values may not qualify as adverse events.

It is the investigator's responsibility to review all laboratory findings. Medical and scientific judgment should be exercised in deciding whether an isolated laboratory abnormality should be classified as an adverse event.

If a clinically significant laboratory abnormality is a sign of a disease or syndrome (e.g., alkaline phosphatase and bilirubin 5 \times ULN associated with cholestasis), only the diagnosis (i.e., cholestasis) should be recorded on the Adverse Event eCRF.

If a clinically significant laboratory abnormality is not a sign of a disease or syndrome, the abnormality itself should be recorded on the Adverse Event eCRF, along with a descriptor indicating if the test result is above or below the normal range (e.g., "elevated potassium," as opposed to "abnormal potassium"). If the laboratory abnormality can be characterized by a precise clinical term per standard definitions, the clinical term should

be recorded as the adverse event. For example, an elevated serum potassium level of 7.0 mEq/L should be recorded as "hyperkalemia."

Observations of the same clinically significant laboratory abnormality from visit to visit should only be recorded once on the Adverse Event eCRF (see Section [5.3.5.4](#) for details on recording persistent adverse events).

